## Time schedule

Fall 2000	Pilot study: Composition and testing of test meals (including some food analyses). Funded by the Council for Development Research, Ministry of Foreign Affairs, Denmark, International Center for Living Aquatic Resources Management, Bangladesh and USAID. Already completed.
Fall 2001	Submission of research project for approval by the Research Review Committee (RRC) and Ethical Review Committee (ERC) of ICDDR,B. Design of forms and questionnaires. Selection of camps and identification of households and target children (inclusion criteria points 1-4, page 12)
Fall 2001 – beginning of January 2002	
Setting up the survey (2 months):
 
 
➤ Organisation of study facilities and development of forms and Questionnaires
 
➤ Recruitment of field staff and training as well as pilot testing of forms and Questionnaires, procedures and equipment
 
➤ Obtaining informed consent from parents (inclusion criteria points 5, page 11)
 

Mid December – beginning of February 2002	
Before screening for vitamin A deficiency:
 
 
➤ Clinical health examination Children fulfilling inclusion criteria listed in points 1-6, page 11:
 
➤ Stool collection and 1st deworming medication, - stool analysis (n≈550)
 
➤ 2nd deworming (2 weeks after the 1st deworming)
 

Mid January 2002 - mid February	
At screening (n≈ 550):
 
 
➤ 10 days after the 2nd deworming: Clinical health examination, anthropometry (age, height, weight and MUAC), blood collection of children, fulfilling inclusion criteria point 7, page 12
 
➤ Analysis of serum retinol from blood: During a period of 6 weeks, the concentration of serum retinol will be analysed from blood of the 550 children of which 180 with marginal vitamin A deficiency (0.35–0.70 µmol/L) will be randomly selected
 

End January 2002 - mid February	
Collection of baseline information of the households and the screened children (n≈ 550):
 
 
- socio-economic data
 
- habitual food and nutrient intake (one 24 h recall interview per child)
 
- risk of dietary vitamin A deficiency (one interview per child)
 
- morbidity data (incidence within the last 30 days, one per child)
 
- data entry
 
 
➤ Training of staff for cooking and feeding
 
Continued on the next page!

## Time schedule (continued)

End February 2002
	
Baseline (n=180):
 
 
➤ Selection of 180 marginal vitamin A deficient children
 
➤ Randomisation of the children to the 3 different intervention groups
 
➤ Clinical health examination, anthropometry (age, weight, height and MUAC), blood collection for the RDR method on a subsample of children (15 in each of The 3 intervention groups)
 

Mid March 2002
	
Feeding period (9 weeks) (n=180):
 
 
➤ Feeding lunch, 6 days a week for 9 weeks to 180 children
 
➤ -Biweekly registration of food intake, beside test meal provided, one 24 h recall interview per child
 
➤ -Biweekly registration of morbidity
 
➤ Collection of duplicate portions of test meals
 

Mid May 2002
	
Endpoint (n≈ 180):
 
 
➤ Clinical health examination, anthropometry (age, height, weight and MUAC), Blood collection of children, RDR test on a subsample of children (15 in each of the 3 intervention groups)
 

June 2002 to October 2002
	
After completion of the feeding trial
 
 
➤ Chemical analyses of blood for assessing vitamin A and iron status, CRP, ACT, prealbumin, analyses of nutrient composition of dishes and data entry
 

November 2002 to end 2003
	
 
➤ Data entry and statistical analyses of data
 
➤ Writing articles for publication in international journals
 
➤ Reports to sponsors and institutions in Bangladesh
 
➤ Presentation of results to organisations/institutions which plan and implement Policies, strategies, programmes and projects for the prevention and reduction of vitamin A deficiency in children in developing countries, especially Bangladesh
 

## Facilities Available

Describe the availability of physical facilities at the place where the study will be carried out. For clinical and laboratory-based studies, indicate the provision of hospital and other types of patient's care facilities and adequate laboratory support. Point out the laboratory facilities and major equipments that will be required for the study. For field studies, describe the field area including its size, population, and means of communications. (TYPE WITHIN THE PROVIDED SPACE).

The study will be conducted in Mirpur slum, Dhaka in a house purposely rented for the study. The building will be used e.g. to conduct the health examination of the children, blood drawing, food storage, cleaning, and preparation, cooking and feeding of test meals to 180 children. In the same building the families of the children will have access to the services of a medical doctor, free of charge during study.

The laboratories at Laboratory Sciences Division, ICDDR,B have the required expertise to perform assays of the study.

The following chemical analyses of blood will be done by Laboratory Sciences Division, ICDDR,B:

Biochemical Indicator	Device and reference
Serum retinol	HPLC, Bieri JG et al. , 1979
Serum retinol binding protein	Single radial immunodiffusion technique using commercial partigen plates (SRID)
Haemoglobin (whole blood)	Colorimetric, Von Klein et al. , 1965
Serum ferritin	Enzyme Immunoassay, Dubois S et al. , 1988
Serum transferrin receptor	Enzyme Immunoassay, Flowers CH et al. , 1989
CRP	Immunoturbidimetric (Roche, commercial kit)
ACT	Immunoturbidimetric (Roche, commercial kit)

The following chemical analyses of dish samples will be done by Laboratory Sciences Division, ICDDR,B and in Denmark:

Nutrient	Device and reference	Place of analysis
Dry matter	Freeze-drying	ICDDR,B
Vitamin A	HPLC, Bail GFM 1988	ICDDR,B
Energy	Bomb Calorimetric, British standard	ICDDR,B
Protein	Micro Kjeldhal, Horwitz ED, 1975	ICDDR,B
Fat	Titration van Dekamer, Van de Kamer JH, 1958	ICDDR,B
Ash	Muffle Furnace	Denmark
Iron, calcium, zinc	Atomic absorption spectrophotometer. AOAC official methods of analysis, 1990	Denmark

The following stool analyses will be done at the Parasitology Laboratory, ICDDR,B:

Type of parasitic infestation	Type of examination
Helminths, Ascaris lumbricoides and Trichuris trichuria	Intensity of infestation (mean eggs/g faeces)
Hookworms	Intensity of infestation (mean eggs/g faeces)
Protozoa cysts, Entamoeba histolytica , Giardia intestinalis and other protozoa cysts	Verification as zero, few, moderate or heavy

The faecal samples will be examined microscopically by the quantitative ether sedimentation technique (Hall, 1981).

## Data Analysis

Describe plans for data analysis. Indicate whether data will be analyzed by the investigators themselves or by other professionals. Specify what statistical softwares packages will be used and if the study is blinded, when the code will be opened. For clinical trials, indicate if interim data analysis will be required to monitor further progress of the study. (TYPE WITHIN THE PROVIDED SPACE).

The first, second and third specific objectives refer to the results from the feeding trial (n=180, one test meal for 9 weeks). The fifth specific objective refers to the results for health, food intake, morbidity and nutritional status from the screening (pre-feeding trial) (n=550).

The data from the feeding trial is longitudinal as in each individual, each indicator is measured more than once over time. For indicators for changes in vitamin A and iron status, analysis of covariance will be used, testing group effect as a factor with nutrient intake during study, initial vitamin A and iron status, changes in iron status, markers of infection, morbidity during study, marker of protein energy malnutrition, initial and/or change in antropometry as covariates. Thus, comparisons of changes in the indicators between the three groups will be analysed (specific objectives one and two). In addition, the effect of the above mention variables on changes in the indicators for vitamin A and iron status will be explored. If an effect is found, sub group analysis will be performed (specific objective three).

In order to study the relationship between the indicators for vitamin A and iron status, parasites, infection, morbidity, food and nutrients intake and anthropometry, (multi)-analysis of variance will be used (specific objective five).

Variance homogeneity of residual variation will be investigated through plots of standardised residuals against predicted values. Normal distribution of data will be investigated graphically and by Wilk-Shapiro's test for normal distribution. If variance homogeneity does not exist or the data are not normally distributed, suitable mathematical transformations will be tried before nonparametric statistical analysis is performed.

The effect of sample size on the results obtained will be explored.

The children (n=550) are given a unique number at *screening*, numbers 300-850.

Children (n=180) who are selected for participating in the feeding trial are randomly assigned to the 3 treatment groups and subsequently given another number; group 1: 001-060, group 2: 061-120 and group 3: 121-180. If more than one measurement is done on the same child of a parameter, the child will be labelled with the above given number followed by another number starting with 1, i.e. **child number - 1**, **child number- 2** .. etc.

The blood analysis will be done without knowledge, of which group the children are assigned, since every blood analysis is given a unique number. The data analysis will be done without knowledge of which intervention group the children are assigned. The groups will be decoded at the completion of the analysis.

The co-principal investigator Ph.D. scholar [name] will do the major statistical analysis. During the statistical analysis of data, a qualified statistician from The Royal Veterinary and Agricultural University, Denmark will give appropriate assistance. A statistician has been involved in the planning of the study design, and the details of the statistical analysis are being developed as the study plan and implementation progress.

The statistical analysis will be performed with the Statistical Analysis System software (SAS Institute, Inc., Cary, NC, USA).

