### Hypothesis to be Tested

An intake of 45g vitamin A rich small fish (mola, *Amblypharyngodon mola*) improves vitamin A status in Bangladeshi preschool children with marginal vitamin A deficiency.

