The negative control group is included because changes in serum retinol over time may be related to factors other than the small fish, such as seasonal variation and infection. The positive control group, receiving pure retinol is included in order to determine the maximal change in serum retinol.

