#### **Calculation of sample size**

Using retinol rich foods, fruit or vegetable, de Pee *et al* (1998a) found an increase in serum retinol of 0.23  $\mu\text{mol/L}$ , 0.12  $\mu\text{mol/L}$ , 0.07  $\mu\text{mol/L}$  respectively from a baseline of approximately 0.70  $\mu\text{mol/L}$  in a 9 weeks' intervention study in children 7-11 y. A dose of 650 RE/d given in two meals daily was used. The maximum standard deviation, 0.17  $\mu\text{mol/L}$  in the change in serum retinol from baseline to the end of the study was found in the fruit group.

The expected increase in serum retinol in the mola group in this study, 0.15  $\mu\text{mol/L}$  is based on an expected increase which is lower than that found in the group given the retinol rich food but higher than that in the group given fruit. Children in the positive control group might show a similar or a larger increase in serum retinol concentration than the mola group.

Assuming similar prevalence and distribution of serum retinol concentration at baseline in Bangladeshis as in the Indonesian children, about 0.70  $\mu\text{mol/L}$  and the expected increase amounts to a 20% increase from the baseline value.

The number of participants in each group,  $n$  is calculated from power calculations based on the following formula (Armitage & Berry, 1987):

$$n = [(Z_{\alpha} + Z_{\beta})^2 * (sd_1^2 + sd_2^2)] / d^2$$

$$Z_{\alpha} = 1.96 \text{ for } \alpha = 0.05, \quad Z_{\beta} = 1.28 \text{ for } \beta = 0.10 \text{ (power of 0.90)}$$

$sd_1, sd_2$  = standard deviation of the change in serum retinol from baseline to the end of the study for group 1 and group 2  $sd_1 = sd_2 = 0.20 \mu\text{mol/L}$

$d$  = difference in change in serum retinol between group 1 and group 2,  $d = 0.15 \mu\text{mol/L}$

The sample size required in each group is 37. Assuming a maximum possible drop out of 40%, the total number of children in each intervention group is calculated to be approximately 60. The total number of children to be used in this study is 180.

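### The only test named for objective one is a three-arm group effect, which a responding positive control makes significant whether or not mola works, and no comparison is named as the deciding one

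*Protocol*

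**What the plan says.** The hypothesis concerns one fish: a daily portion of mola "improves vitamin A status in Bangladeshi preschool children with marginal vitamin A deficiency". The Overall aim and the first specific objective set the change under mola against the change under rui, and also against the change under rui with added retinyl palmitate.

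Calculation of sample size powers a single two-group quantity, the "difference in change in serum retinol between group 1 and group 2". That section does not say which arms these are. The list in Design and intervention groups puts mola first and rui second, which suggests mola versus rui, but the sample-size text does not make the link.

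Data Analysis names one test for the feeding trial: "analysis of covariance will be used, testing group effect as a factor", with a list of covariates. It continues: "Thus, comparisons of changes in the indicators between the three groups will be analysed (specific objectives one and two". No pair of arms is singled out. The same section says that the data are analysed without knowledge of the intervention groups and that the groups are decoded when the analysis is complete.

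On the third arm, Design and intervention groups says: "The positive control group, receiving pure retinol is included in order to determine the maximal change in serum retinol". The sample-size section expects it to rise about as much as mola, or more.

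**The concern.** A test of a three-level factor asks whether any arm differs from the others. One arm here was added because it should raise serum retinol. If it does, the group factor is likely to be significant for that reason alone, whatever mola does. The only test named for objective one could then be reported as a significant effect of diet group in a trial where mola did nothing. It is also not the two-group difference for which 90% power was calculated.

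Blinding adds a practical difficulty. An analyst who does not know the codes can run the overall test or all three pairs. That analyst cannot single out mola versus rui unless the coded pair has been designated beforehand.

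**Working it through.** **Inputs.** From Calculation of sample size: two-sided alpha 0.05 (z = 1.96), power 0.90 (z = 1.28), SD of change 0.20 µmol/L in each group, difference 0.15 µmol/L, 37 per group, drop-out up to 40%, 60 enrolled per group. For the positive control, the lower anchor is 0.15 (the rise expected with mola, which this arm should match or exceed). The upper anchor is 0.23 (the rise with retinol-rich food in the cited Indonesian trial). I take rui as unchanged, so that these rises are also differences from rui.

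**1. The plan's own figure.** n = (1.96 + 1.28)² × (0.20² + 0.20²) / 0.15² = 10.4976 × 0.08 / 0.0225 = 37.3, which agrees with the stated 37. Allowing for 40% loss, 37 / 0.6 = 61.7, against the stated approximate 60. Sixty enrolled with 40% lost leaves 60 × 0.6 = 36. The sample size holds as a two-group calculation.

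**2. The group test when mola equals rui.** Take mean changes of (0, 0, δ) for rui, mola and positive control. The F test has 2 and 3(n − 1) degrees of freedom and non-centrality λ = n × (2/3) × δ² / SD². For n = 37 and δ = 0.15, λ = 37 × (2/3) × 0.0225 / 0.04 = 13.9. Probability that the group effect is significant at 5%, with SD 0.20:

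| Rise in positive control (µmol/L) | n = 36 | n = 37 | n = 60 |
|---|---|---|---|
| 0.10 | 57.1% | 58.4% | 80.8% |
| 0.15 | 91.1% | 91.8% | 99.2% |
| 0.23 | 99.94% | 99.95% | >99.9% |

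With SD 0.17, the largest SD quoted from the cited trial, a rise of 0.15 gives 97.9% at n = 37 and 99.9% at n = 60. A simulation of 20,000 trials at n = 37 and SD 0.20 gave 92.2% for a rise of 0.15 and 99.9% for 0.23.

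**3. The group test when mola works.** With mean changes (0, 0.15, 0.15), the sum of squared deviations is again (2/3) × 0.15². So λ and the rejection rate are the same as in step 2: 91.8% at n = 37. The overall test rejects equally often whether mola does nothing or does all that was hoped.

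**4. The mola-minus-rui contrast.** The non-centrality is 0.15 / (0.20 × √(2/n)), which is 3.23 at n = 37 and 4.11 at n = 60. Using the pooled three-arm error, power is 89.2% and 98.3%. With mola equal to rui, the contrast was significant in 4.6% and 5.0% of simulated trials (positive control at +0.15 and +0.23).

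**5. The addendum's preliminary means.** Changes are 0.60 − 0.59 = +0.01 for mola, 0.84 − 0.59 = +0.25 for the positive control and 0.65 − 0.60 = +0.05 for rui. The SD of change is not given. Assuming 0.15 to 0.30 and 37 to 60 per arm, true means of this size would make the group test significant 91% to 100% of the time, although mola rose less than rui.

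**The case against.** The strongest reply is that the comparison is already in the protocol. The Overall aim and objective one say that mola is compared with rui and with the positive control, and Data Analysis ties its plural comparisons to that objective. On this reading, the phrase about the group factor only describes how group enters the model, and pairwise contrasts follow. Nothing says that a significant overall test counts in favour of mola. The simulation supports part of this reply: requiring a significant group test and then a significant mola-rui contrast still gave a false-positive rate of about 5% for that contrast (4.6% and 5.0%). Naming the primary contrast is also often left to a statistical analysis plan, and Data Analysis says its details are still being developed.

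Much of this stands. A reader might infer that the trial does not test its hypothesis, or that the positive control guarantees a significant result. The documents support neither. The mola-rui comparison is described in words, and at a rise of 0.10 the group test is far from certain to reject. Nor does the addendum show misuse: it reports before-after results arm by arm and says that the improvement was less than expected.

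The reply leaves two things open. The one test that the protocol does name is the three-arm one, and it is attached to objectives one and two. Objective one also gives mola two comparators without saying which decides, and the two answer different questions.

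**Conclusion.** The point holds as an unfixed decision attached to a poorly chosen named test. Over the range of positive-control response that the protocol's own figures imply, a significant group effect says almost nothing about mola.

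The percentages assume normal changes with equal SD, no change under rui, and no covariates. Covariates that reduce the residual SD would raise them. One covariate could invalidate them: nutrient intake during the study. Objective three bases it on dietary recall, which the Food intake section uses for foods outside the test meals, but that section also computes a total that includes the test meals. If that total entered the model, it would absorb part of the added vitamin A.

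The design and sample size need no change, since the mola-rui contrast has about 89% power at 37 per arm. This should be corrected in the protocol because it alters a stated test, but it is not a fatal flaw.

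**What to change.** In Data Analysis, state that objective one is decided by one contrast from the covariance model: the adjusted mola-minus-rui difference in change in serum retinol, tested two-sided at 5% and reported with its 95% confidence interval. Say that the overall group test is not evidence for mola.

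Report positive control minus rui as the check that the trial could detect a response. Report mola versus positive control as an estimate with its interval. If that comparison were also to be tested with alpha split equally, power for mola versus rui would be 82.8% at 37 per arm and 96.7% at 60.

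In Calculation of sample size, name mola and rui as groups 1 and 2. Before the blinded analysis, have someone outside it designate which coded pair is the deciding one.

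The cost is a few sentences, with the same model, data and number of children.

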### Specific objectives

- To assess the efficacy of vitamin rich small fish, mola in improving vitamin A status (based on serum retinol concentrations, results from the Relative Dose Response (RDR) method, serum retinol binding protein and prealbumin concentrations). This will be done by comparing the increase in vitamin A status after supplementation of mola fish with the increase in vitamin A status after supplementation of non/low vitamin A rich big fish, rui and supplementation of rui with added retinyl palmitate, in a daily meal for 9 weeks to marginally vitamin A deficient children (3-7 y) in a Dhaka slum.
- To investigate the impact of intake of vitamin A rich small fish on iron status (based on haemoglobin, serum ferritin and serum transferrin receptor) in children in comparison with that of non/low vitamin A rich big fish and non/low vitamin A rich big fish with added retinyl palmitate.
- To investigate whether the factors: a) nutrient intake during study (based on repeated 24 h recall interview), b) initial vitamin A and iron status, c) changes in iron status, d) markers of infection (based on C-reactive protein (CRP) and  $\alpha$ -1 anti-chymotrypsin (ACT)), e) morbidity during study (based on incidence of infection such as diarrhoea, acute respiratory infections, fever, measles and night blindness), f) marker of protein energy malnutrition (based on prealbumin), g) initial and/or change in nutritional status (based on height, weight, MUAC) affect the change in vitamin A status after intake of vitamin A rich small fish in comparison with that of intake of non/low vitamin A rich big fish and non/low vitamin A rich big fish with added retinyl palmitate. In addition, if an effect is seen it will be investigated whether some subgroups benefit more than others from the intervention.
- To investigate qualitatively the mothers' perceptions of the effect of the mola supplementation on the general well being of the children as well as the acceptance of mola for habitual use among the children and their families.

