### Study population and subjects

Preschool children, age 3-7 y of both sexes will be selected from the urban slum in Mirpur, a suburb of Dhaka which is 10 km from the International Centre for Diarrhoeal Disease Research, Bangladesh (ICDDR,B): Centre for Health and Population Research. Mirpur slum is subdivided into camps covers a large area with a very high population density and poor housing. It is estimated that more than 3,000 children between 3 and 7 y live in the study area. Both the subjects and the study area are suitable for this study. Preschool children are known to suffer from the major health effects of vitamin A deficiency. Data from 2 merged studies have shown that children 3-6 y in Mirpur slum have a high prevalence of vitamin A deficiency, 53% (n=286) had serum retinol concentrations below  $< 0.70 \mu\text{mol/L}$ , even though there is a national vitamin A programme of biannual capsule supplementation. The prevalence of vitamin A deficiency (serum retinol concentrations below  $< 0.70 \mu\text{mol/L}$ ) subdivided into age groups was: 3-4 y, 49% (n=145); 4-5 y, 58% (n=128); and 5-6 y, 56% (n=13), respectively ([name] *et al.*, 1998; [name] *et al.*, 2001).

Mola is not eaten frequently in the study area and assembling this age group in one place in order to serve one meal per day is considered most appropriate. The study site and population are already familiar to ICDDR,B, being used for different health research studies which have been conducted or are presently being carried out. ICDDR,B has a local office in the Mirpur slum, which employs both ICDDR, B professionals and local community people. There are good infrastructure, records of the area and households as well as a good rapport and collaboration with the community leaders and inhabitants. The short distance from the study area to the ICDDR,B facilities (with electricity, laboratory, storage and freezer) is crucial for carrying out the study successfully.

The selected children will be randomly across age range and gender and the children enrolled in the study will be randomly allocated to three intervention groups. Differences in age and gender are not expected to effect the output of the study. However, the effect of these variables will be taken into consideration in the statistical analysis.

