### **Confounding factors**

Since the outcome of the intervention study may be affected by factors other than the fish consumed, the confounding variables markers of infection and protein energy malnutrition as well as anthropometry, food intake, morbidity as described below will be measured during study and adjusted for in the statistical analysis.

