### **Food intake**

One 24 h dietary recall of all 550 children will be conducted as baseline information in order to assess habitual food and nutrient intakes at the group level. In addition, a semi-quantitative dietary assessment of vitamin A intake will be done in order to assess the risk of inadequate dietary vitamin A intake at the group level.

During the feeding trial, between *baseline* and *endpoint*, intakes of nutrients (vitamin A as well as energy, carbohydrate, protein, fat, iron, zinc and calcium) from foods not provided in the test meals will be calculated from biweekly food consumption surveys of the 180 children, using the 24 h recall method.

The results will be used to calculate the total daily intakes of nutrients in each treatment group during the feeding trial based on the following:

1) data from the food consumption surveys conducted between *baseline* and *endpoint* (mean of 4-5 dietary recalls) and 2) the amount of food given in the dishes (corrected for leftovers) and from the chemical analyses of duplicate samples of the dishes (please see below).

The total daily intakes of nutrients during feeding trial will be compared between treatment groups as well as with habitual food and nutrient intake.

The conduction of the 24 h recall method will be based on the method described by Gibson, 1990. The questionnaire is enclosed as Appendix 5.

The method used for conducting the semi-quantitative dietary assessment of vitamin A intake will be based on the method proposed by the International Vitamin A Consultative Group (IVACG) (Underwood *et al*, 1989). The questionnaire is enclosed as Appendix 4.

The health assistants will be trained, the questionnaires will be pre-tested, the health assistants will be checked in the field by supervisors and the filled out questionnaires will be checked daily.

A random check of 5% of the total number will be conducted in order to test the reliability of the 24 h dietary recalls, semi-quantitative assessment of vitamin A intake and morbidity questionnaires. This means that another person repeats the visit in the same household on the same day for 5% of the households. A quick comparison of the field assistant's questionnaire and the supervisor's questionnaire is done on the same day. At *baseline*, the field system may be adjusted to correct the faults.

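### The efficacy ANCOVA adjusts the group effect for variables measured after randomisation, so it does not estimate the total mola-versus-rui difference on which the trial was sized

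*Protocol*

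**What the plan says.** The Data Analysis section of the protocol sets one model for changes in the vitamin A and iron indicators: "analysis of covariance will be used, testing group effect as a factor with nutrient intake during study", followed by initial vitamin A and iron status and then "changes in iron status, markers of infection, morbidity during study, marker of protein energy malnutrition, initial and/or change in antropometry as covariates". The next sentence ties this model to efficacy: "Thus, comparisons of changes in the indicators between the three groups will be analysed (specific objectives one and two". Exploring how the covariates act on the outcomes comes afterwards, as an additional step under objective three. No unadjusted comparison and no comparison using baseline covariates only is stated.

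The section on confounding factors repeats the commitment. It names markers of infection and of protein energy malnutrition and continues: "anthropometry, food intake, morbidity as described below will be measured during study and adjusted for in the statistical analysis".

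Other sections give several of these variables a second role. Specific objective one measures vitamin A status partly by "serum retinol binding protein and prealbumin concentrations", while objective three and the section on biochemical markers use prealbumin as the malnutrition marker. Objective two has iron status as its outcome. The Background says that better vitamin A status makes infectious illness less severe and may improve iron status, and the Project Summary describes small fish as rich in iron.

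**The concern.** Randomisation makes the groups comparable at the start. A variable that arises afterwards cannot confound the group comparison, but it can lie on the path from the test meal to serum retinol, or be a consequence of the change in retinol. Holding it fixed changes the question. The group coefficient then describes the mola effect that remains among children with the same change in iron, the same morbidity and the same prealbumin. The hypothesis asks whether mola improves vitamin A status by whatever route, and the model does not answer that.

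By the protocol's own rationale, iron status and morbidity should respond to vitamin A, and prealbumin is one of the indicators by which success is judged. Adjusting for such variables would be expected to shrink a real mola effect. A true benefit could then be reported as small or absent in the only efficacy comparison that the protocol states.

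**Working it through.** **1. The plan's own figure.** Inputs from Calculation of sample size: Zα = 1.96, Zβ = 1.28, SD of change 0.20 µmol/L in each group, d = 0.15 µmol/L.

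n = (1.96 + 1.28)² × (0.20² + 0.20²) / 0.15² = 37.3, stated as 37. With 40% dropout, 37 / 0.6 = 61.7, stated as approximately 60. Both reproduce. The formula contains no covariates: d is the total between-group difference in change.

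**2. Timing and role of each covariate.**

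| Covariate | Timing | Other role in the protocol |
|---|---|---|
| Initial vitamin A and iron status | before randomisation | none; sound |
| Nutrient intake during study | after | none |
| Change in iron status | after | outcome of objective two |
| Morbidity during study | after | expected to respond to vitamin A (Background) |
| Prealbumin | taken at screening and endpoint; Data Analysis does not say which | indicator in objective one |
| Anthropometry, initial and/or change | before and/or after | none |
| CRP, ACT | taken at screening and endpoint | mark the infection that lowers measured retinol |

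**3. What the adjusted model estimates.** Let M stand for the post-randomisation covariates, a for the effect of group on M, and b for the effect of M on change in retinol. The total effect is d = direct + ab. With M in the model, the group term estimates the direct part only, d(1 − m), where m = ab/d is the share carried by M. The documents do not give m, so the values below are assumptions.

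**4. Illustration.** Power = Φ( d(1 − m) / (0.20 × √(2/n)) − 1.96 ). The standard error is 0.0465 at n = 37 and 0.0365 at n = 60. For example, with m = 0 and n = 37: 0.15 / 0.0465 − 1.96 = 1.27, giving 89.7%.

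| Assumed m | Effect estimated (µmol/L) | Power, 37 per group | Power, 60 per group |
|---|---|---|---|
| 0 | 0.150 | 90% | 98% |
| 10% | 0.135 | 83% | 96% |
| 20% | 0.120 | 73% | 91% |
| 30% | 0.105 | 62% | 82% |
| 50% | 0.075 | 36% | 54% |

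**5. Check by simulation.** 4,000 trials were simulated for each m at 37 per group, with an assumed within-group correlation of 0.4 between M and the outcome. The unadjusted estimate stayed at about 0.15. The adjusted estimate was 0.135, 0.119, 0.105 and 0.075 for m = 10%, 20%, 30% and 50%, with power 87%, 77%, 64% and 34%. With m = 0, adjustment raised power from 89% to 93%, because the covariate removed residual variance. The loss therefore depends on whether mola moves the covariates.

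**The case against.** Several points on the other side stand.

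- The choice was considered. A funder's referee suggested infection, morbidity, food intake and anthropometry as covariates where appropriate, and the investigators agreed. The protocol adds that details of the analysis were still being developed. This explains the model but does not change what it estimates.
- The shares of 10% to 50% are assumed, and conditioning on post-randomisation variables can bias in either direction. Moreover, 37 per group is the floor after the maximum dropout; at 60 per group the loss is smaller.
- CRP and ACT differ from the other covariates. The protocol notes that infection artificially lowers serum retinol, so adjusting for endpoint values is defensible.
- The anthropometry wording permits initial values only.
- Age and sex are absent from the covariate list, but they are not forgotten. The section on study population says that "the effect of these variables will be taken into consideration in the statistical analysis".

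Three stronger readings are tempting, and the documents do not support them.

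- A reader might infer that the intake covariate contains the vitamin A of the test meal, so that the model adjusts for the treatment itself and the group effect collapses to near zero. The Food intake section does build such a total: "The results will be used to calculate the total daily intakes of nutrients in each treatment group". But objective three bases its intake factor on 24 h recalls, and the Food intake section and the Time schedule confine those recalls to food outside the test meal. The total is for comparison between groups and with habitual intake. Home intake is still measured after randomisation, but it is not the intervention.
- A reader might infer that change in iron is adjusted for itself. Objective three lists it as a factor for change in vitamin A, which is the sensible reading.
- A reader might link the model to the flat preliminary mola result in the later addendum (0.59 to 0.60 µmol/L). Those are pre and post group means, with only an acute-phase correction mentioned, so that result cannot be traced to this ANCOVA.

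**Conclusion.** The concern holds in a limited form. The stated efficacy model for objectives one and two conditions on intake during the study, change in iron status, morbidity and, as the text allows, endpoint prealbumin and change in anthropometry. It therefore does not estimate the total randomised difference of 0.15 µmol/L on which the trial was sized. This follows from the protocol's wording and needs no outside figure.

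The consequence is less certain. Attenuation is the likely direction if, as the protocol expects, better vitamin A status alters these variables and they are in turn tied to retinol. The documents do not allow its size or direction to be computed. The power figures are conditional illustrations, and there is no loss from this source if mola leaves the covariates unchanged.

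**What to change.** Reword the model paragraph in Data Analysis, and the matching sentence under confounding factors, as follows.

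- **Objectives one and two:** ANCOVA of the change in each indicator with group as factor and only pre-randomisation covariates: the screening value of that indicator, initial iron status, initial anthropometry, age, sex, and screening CRP and ACT.
- **Alongside:** the same model with endpoint CRP and ACT added, because infection lowers measured retinol. Present it next to the main result, not in its place, since vitamin A may itself influence infection.
- **Objective three, labelled exploratory:** all models containing during-study intake, morbidity, change in iron status, change in anthropometry or endpoint prealbumin. State there that the intake variable comes from the recalls and excludes the test meal.

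The cost is one rewritten paragraph and slightly more analysis. Every variable is already to be collected. Some precision that the during-study covariates would have added may be lost: in the simulation with no mediation, the difference was 93% against 89% power at 37 per group.
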